### 7.10.2 CCI

CCI

## 7.11 Safety Analysis

All summaries of safety data are based on subjects in the Safety Analysis Set. Unless otherwise specified, the safety data will be summarized by trial group. Unless otherwise stated, data imputation will not be performed for any missing safety data.

### 7.11.1 Adverse Events

For summaries of solicited and unsolicited AEs only subjects from the immunogenicity subset will be included. SAEs will be summarized for all subjects.

### Reactogenicity (Solicited AEs)

Solicited local AEs (infant/toddler/child < 6 years: injection site pain, injection site erythema and injection site swelling; adult and child  $\geq$  6 years: injection site pain, injection site erythema and injection site swelling) and solicited systemic AEs (infant/toddler/child < 6 years: fever, irritability/fussiness, drowsiness and loss of appetite; adult and child  $\geq$  6 years: asthenia, body temperature, headache, malaise, myalgia) will be assessed for 7 and 14 days following each vaccination (vaccination day included), respectively, via collection of diary cards.

The presence and severity of each solicited symptom will be collected using diary cards. The subject will record the severity of each AE (except erythema, swelling and temperature) according to the diary card instruction as none, mild, moderate, or severe. These grades will be entered onto the eCRF. For the local AEs erythema and swelling, the subject will record the length of the longest diameter. For the systemic AE fever, the subject will record the temperature in either degrees Fahrenheit or degrees Celsius. Severity grades for erythema and swelling will be derived from the recorded lengths, and fever will be derived from the recorded temperature measurements using guidance published by the Brighton Collaboration[2].

The details of Solicited local and systemic AEs, Intensity scales for solicited AEs in infants/toddlers (15-24 months)/child (< 6 years) and Intensity scales for solicited AEs in adults/children ( $\geq$  6 years) are given in [Appendix B](#).

For each solicited AE, the summary tables will be presented by each age category, infants/toddlers (15-24 months)/child (< 6 years) and adults/children ( $\geq$  6 years). The percentage of subjects will be summarized by event severity for each day (Days 1 to 7 and Days 1 to 14 after each vaccination for local and systemic AEs, respectively) and overall.

For solicited AEs, missing data will be handled as follows. For each group and solicited AE, the denominator for the percentage will exclude subjects with completely missing data (i.e. subject does not have at least one recorded results of none, mild, moderate, or severe) for the solicited AE in the period being summarized.

A summary of the first onset of each event will also be provided. The number of days subjects experienced each event will also be summarized for each group. For subjects with more than 1 episode of the same event, the maximum severity will be used for tabulations.

### Unsolicited AEs

Unsolicited AEs and SAEs, will be coded according to the Medical Dictionary for Regulatory Activities (MedDRA) and summarized by system organ class (SOC) and preferred term (PT) for each treatment arm. AEs leading to trial or vaccine withdrawal will also be summarized.

All unsolicited AEs up to 28 days after the last vaccination will be included in the analyses of all AEs. For SAEs and AEs leading to subject withdrawal from the trial, any AE collected during the trial will be included. In general, unsolicited AEs will be tabulated at each of the following levels: overall summary (subject with at least 1 AE) and by SOC and PT. Subjects reporting more than 1 occurrence for the term (level) being summarized will be counted only once.

Unsolicited AEs will be summarized as follows: by PT including events with frequency greater

than 2%; by SOC and PT; by SOC, PT, and severity; and by SOC, PT, and relationship to the investigational vaccine. Unsolicited AEs will be summarized as described above for the following periods:

1. Onset within 28 days after vaccination 1
2. Onset within 28 days after vaccination 2
3. Onset within 28 days after vaccination 3
4. Onset within 28 days after any vaccination
5. Onset between 1 and 14 days after vaccination 1
6. Onset between 1 and 14 days after vaccination 2
7. Onset between 1 and 14 days after vaccination 3
8. Onset between 1 and 14 days after any vaccination
9. Onset between 15 and 28 days after vaccination 1
10. Onset between 15 and 28 days after vaccination 2
11. Onset between 15 and 28 days after vaccination 3
12. Onset between 15 and 28 days after any vaccination

Similar summaries by baseline seropositive status will also be included.

In addition, a summary of most frequent non-serious unsolicited AEs will be prepared by SOC and PT including events with frequency greater than 2% to provide this information for Clinicaltrials.gov.

### **7.11.2 Clinical Laboratory Evaluations**

Not applicable

### **7.11.3 Vital Signs**

The vital signs collected in the trial include systolic and diastolic blood pressure, heart rate, body temperature, and weight and height. Note that height will only be measured at Visit 1 [Day 1 (M0)]. Vital signs will be summarized descriptively with windowed visits, and individual subject data will be presented in the listing by group, site, subject number, collection date/time, and measurement parameters. The measurement parameters will be sorted or grouped in a clinically meaningful order.

Measurements are taken at Day 1 (M0), Day 28 (M1), Day 91 (M3), Day 180 (M6), Day 365 (M12), Day 393 (M13), Day 540 (M18), Day 730 (M24), Day 1095 (M36), and Day 1460 (M48).

Descriptive statistics (N, mean, median, SD, minimum and maximum) of vital sign parameters (observed and change from baseline) except the height will be summarized by trial group at each visit. Only vital sign measurements at the scheduled visits will be included in the summaries.

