### **Definition of Baseline and Windowing of Post Baseline Data:**

Baseline is defined as the last non-missing measurement taken before the first dose of vaccination. Trial Day 1 is defined to be the date of the first vaccination, as recorded on the CRF vaccination page. Other trial days are defined relative to the trial day 1, with Day -1 being the day prior to Day 1.

A windowing convention will be used to determine the analysis value for a given trial visit for observed data analyses and will be applied to immunogenicity data, vital signs, CCI [REDACTED]. The window definitions are defined below in **Table 7.a** by trial visit. The window conventions are consecutive and contiguous; that is, the lower or upper bound of the windows is the midpoint between 2 consecutive trial visits and all data are included.

If more than one result for a variable is obtained for a subject in a visit window, the result with the date closest to the scheduled/expected visit date will be used. In the event that two measurements within a given visit window are equidistant to the scheduled visit date, the later observation will be used.

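### The vital-sign column of SAP Table 7.a stops at an open-ended Month 18 window, so the Month 24, 36 and 48 summaries required by Section 7.11.3 have no window

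*SAP*

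**What the plan says.** Three parts of the SAP bear on which visit a vital-sign record belongs to.

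- **Section 7.1, baseline and windowing.** The windowing convention "will be applied to immunogenicity data, vital signs" (and a further redacted data type). The windows are contiguous: "the lower or upper bound of the windows is the midpoint between 2 consecutive trial visits and all data are included". When a subject has several results in one window, "the result with the date closest to the scheduled/expected visit date will be used".
- **Table 7.a.** The vital-sign and immunogenicity columns agree from baseline through Month 13 (380-466). At Month 18 they part: vital signs has ≥ 467 with no upper bound, immunogenicity has 467-635. For Months 24, 36 and 48 the immunogenicity column has 636-912, 913-1277 and ≥ 1278. The vital-sign column has nothing.
- **Section 7.11.3.** "Vital signs will be summarized descriptively with windowed visits". The measurement days include "Day 540 (M18), Day 730 (M24), Day 1095 (M36), and Day 1460 (M48"). Observed values and changes from baseline, height excepted, "will be summarized by trial group at each visit".

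The schedules in Appendix A agree with Section 7.11.3. Tables A-1 and A-2 both mark the brief physical assessment at Months 24, 36 and 48, and their footnotes say that it includes vital signs.

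**The concern.** Section 7.11.3 requires windowed summaries at Months 24, 36 and 48, and the table that defines the windows has no place for them. An open bound at day 467 takes in every later day, so a program written from the table cannot place a record at any of the last three visits.

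Two consequences follow if the table is applied as printed. The vital-sign summaries at those visits are lost. And a subject with no Month 18 measurement but a later one would have that later value shown under Month 18, in a population aged 2 to under 18 years in whom weight, for one, changes with growth. A programmer would have to choose between the table and the text, and the SAP should settle that choice beforehand.

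**Working it through.** **Inputs.** Scheduled post-baseline days 28, 91, 180, 365, 393, 540, 730, 1095 and 1460 (Table 7.a and Section 7.11.3). Visit tolerance of ±15 days at Months 18 to 48 (Tables A-1 and A-2). Midpoint and closest-date rules (Section 7.1).

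**Step 1: reproduce the printed bounds.** The bound between consecutive post-baseline visits is (d₁ + d₂)/2, rounded down to give the last day of the earlier window.

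| Visits | Midpoint | Rule closes earlier window at | Immunogenicity column | Vital-sign column |
|---|---|---|---|---|
| M1 / M3 | (28 + 91)/2 = 59.5 | 59 | 59 | 59 |
| M3 / M6 | (91 + 180)/2 = 135.5 | 135 | 135 | 135 |
| M6 / M12 | (180 + 365)/2 = 272.5 | 272 | 272 | 272 |
| M12 / M13 | (365 + 393)/2 = 379 | 379 | 379 | 379 |
| M13 / M18 | (393 + 540)/2 = 466.5 | 466 | 466 | 466 |
| M18 / M24 | (540 + 730)/2 = 635 | 635 | 635 | open |
| M24 / M36 | (730 + 1095)/2 = 912.5 | 912 | 912 | none |
| M36 / M48 | (1095 + 1460)/2 = 1277.5 | 1277 | 1277 | none |

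The rule reproduces every immunogenicity bound between post-baseline visits, and every vital-sign bound up to day 466. After that the vital-sign column departs from it.

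**Step 2: place the later visits in the printed vital-sign windows.** Distance is counted from day 540.

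| Visit | On-time days (±15) | Printed vital-sign window | Distance at nominal day | Range of distance |
|---|---|---|---|---|
| M18 | 525-555 | M18 | 0 | 0-15 |
| M24 | 715-745 | M18 | 730 − 540 = 190 | 175-205 |
| M36 | 1080-1110 | M18 | 1095 − 540 = 555 | 540-570 |
| M48 | 1445-1475 | M18 | 1460 − 540 = 920 | 905-935 |

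**Step 3: apply the closest-date rule.** An on-time Month 18 value lies at most 15 days from day 540. The nearest competitor, an on-time Month 24 value, lies at least 175 days away. So the true Month 18 value is kept whenever it exists, and the later values drop out of the summaries. If it is missing, the earliest available later value is shown as Month 18. A Month 48 value appears there only if Months 18, 24 and 36 are all missing.

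**Step 4: repeat with the immunogenicity bounds.** Days 715-745, 1080-1110 and 1445-1475 fall in 636-912, 913-1277 and ≥ 1278, so each visit is placed under its own label.

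**Who is affected.** Subjects in the immunogenicity subset (600) have ten visits and would lose three. The other 1,800 − 600 = 1,200 have seven visits and would also lose three.

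**The case against.** The best defence is that the text already settles the matter. The midpoint rule, applied to the listed visit days, gives the right windows, and Section 7.11.3 names all ten visits. A careful programmer would see that the table cell is the odd one out, so the losses in the working are possible outcomes and not certain ones. That is fair as to likelihood. It does not remove the point: the table is the operative list of windows, it states a bound that contradicts the rule, and the SAP does not say which prevails.

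The blank cells might be thought a redaction. The redaction marks in Table 7.a stand only in the last column, and a printed bound of ≥ 467 leaves no days for any later window. They might be thought a deliberate decision to stop windowing vital signs at Month 18, but the current text of Section 7.11.3 and both schedules say otherwise. More likely, though this is inference, the column was left over when the trial was extended to Month 48.

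The stakes are low, and this stands. Vital signs are not among the primary or secondary endpoints in Section 5, the trial is descriptive, and individual values are listed with collection date and time. The interim analyses use only data up to Month 6 and Month 18, so they are essentially untouched.

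A reader might also see a second conflict between windowed visits and the sentence "Only vital sign measurements at the scheduled visits will be included in the summaries". The documents do not support that. The sentence selects which records enter, and windowing decides the visit under which they are shown. The two work together.

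**Conclusion.** Table 7.a is wrong as written for vital signs from Month 18 onward. It contradicts the midpoint rule of Section 7.1 and the visit-by-visit summaries of Section 7.11.3. Applied as printed, its main effect is the loss of the Month 24, 36 and 48 vital-sign summaries. Its lesser effect is mislabelling for subjects with no Month 18 value: nominally 190 days late from Month 24, 555 from Month 36 and at worst 920 from Month 48. How many subjects that would be cannot be derived from the SAP.

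Two stronger readings should be resisted. One is that values from Months 18 to 48 would be pooled: only one value per subject is analysed, the one closest to day 540. The other is that Month 18 changes from baseline are biased in general: the true Month 18 value is used whenever it exists.

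The conclusion assumes that the program follows the table and that visits occur within their tolerances. It touches descriptive vital-sign tables only. The listings, the immunogenicity windows and the GMT endpoint are unaffected.

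**What to change.** In the vital-sign column of Table 7.a, replace ≥ 467 at Month 18 with 467-635 and enter 636-912 for Month 24, 913-1277 for Month 36 and ≥ 1278 for Month 48. These are the values that the SAP's own midpoint rule gives and that the adjacent immunogenicity column already carries. Section 7.11.3 needs no change.

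The cost is one cell corrected and three filled. Data collection, the visit schedule and the other windows stay as they are. The correction should be made before the vital-sign tables for the final analysis are programmed.

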#### 7.11.4 12-Lead ECGs

Not applicable

#### 7.11.5 Other Observations Related to Safety

##### Febrile Illness Follow-Up

Any subject with febrile illness (defined as temperature  $\geq 38^{\circ}\text{C}$  on 2 consecutive days) will be asked to return to the site for dengue fever evaluation. A dengue infection will be considered virologically confirmed by either PCR or NS1 ELISA.

The percentage of subjects with virologically confirmed dengue (based on the febrile illness cases) will be summarized by group and by baseline seropositive status. Frequency tables will show the following three categories: (1) number of virologically confirmed dengue cases with onset before Day 30, (2) number of virologically confirmed dengue cases with onset on or after Day 30 and (3) total number of virologically confirmed dengue cases.

A blood sample will be collected within ( $\leq$ ) 5 days after the onset of fever to perform virological confirmation of dengue and for haematology (white cell count and differential (WCC), platelet cell count (PCC) and hematocrit (HCT)) and biochemistry (Aspartate Transaminase (AST) and Alanine Transaminase (ALT)) to assess the severity of infection. Haematology and biochemistry will be performed by local laboratories. The subject's medical condition will be recorded in the eCRF, including but not limited to headache, rash, abdominal pain, myalgia, arthralgia, signs of bleeding (including petechiae), signs of plasma leakage. WCC and differential, PCC, HCT, AST and ALT will also be recorded, even if values are normal. Summary tables for subjects with virologically confirmed dengue will be provided by group and by baseline seropositive status.

All individual laboratory data will be presented in both SI and conventional (CV) units in the subject data listings by group, site, subject number, collection date/time, and measurement parameter. The measurement parameters will be sorted or grouped in a clinically meaningful order.

For the subset of subjects with virologically confirmed dengue the main summary tables for GMTs and seropositivity rates will be repeated based on the PPS.

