## 4.4 Trial Design

This is a Phase II, double-blind, controlled, randomized trial that will enroll 1,800 healthy children aged 2≥ to <18 years old into 1 of the following 4 groups:

- **Group 1 (TDV 2-dose):** receiving a two-dose primary vaccination at Day 1 (M0:Month 0) and Day 91 (M3:Month 3) with the trial vaccine. These subjects will also receive a placebo injection at Day 365 (M12:Month 12).
- **Group 2 (TDV 1-dose):** receiving a one-dose primary vaccination at Day 1 (M0) with the trial vaccine. These subjects will also receive a placebo injection at Day 91 (M3) and Day 365 (M12).
- **Group 3 (TDV 1-dose with booster):** receiving a one-dose primary vaccination at Day 1 (M0) and booster vaccination at Day 365 (M12) with the trial vaccine. These subjects will also receive a placebo injection at Day 91 (M3).
- **Group 4 (Placebo Control):** receiving injections of placebo at Day 1 (M0), Day 91 (M3), and at Day 365 (M12).

Subjects will be randomized to these 4 groups in a 1:2:5:1 ratio as shown in [Table 4.a](#).

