**Table 4.a Number of Subjects per Group**

Group	No. of Subjects	No. of Subjects in the Immunogenicity Subset
Group 1	200	100
Group 2	400	200
Group 3	1,000	200
Group 4	200	100
Total	1,800	600

Randomization will be stratified by age group based on the age at the time of informed consent:

1. 2 to 5 years of age, inclusive,
2. 6 to 11 years of age, inclusive, and
3.  $12 \geq$  to  $<18$  years of age

CCI

Safety evaluation will include documentation of Serious Adverse Events (SAEs) and identification of febrile episodes of potential dengue etiology in all subjects for the trial duration. In addition, all subjects in the immunogenicity subset will be provided with a diary card and will be instructed to record:

- Solicited local adverse events (AEs) for 7 days following vaccination (day of vaccination + 6 days). These will include:
  - infant/toddler/child  $< 6$  years: injection site pain, injection site erythema and injection site swelling.
  - adult and child ( $\geq 6$  years): injection site pain, injection site erythema and injection site swelling.
- Solicited systemic AEs for 14 days following vaccination (day of vaccination + 13 days). These will include:
  - infant/toddler/child  $< 6$  years: fever, irritability/fussiness, drowsiness and loss of appetite.
  - adult and child ( $\geq 6$  years): asthenia, fever, headache, malaise, myalgia.
- Unsolicited AEs for 28 days following vaccination (day of vaccination + 27 days).

Any subject with febrile illness (defined as temperature  $\geq 38^\circ\text{C}$  on 2 consecutive days) will be asked to return to the site for dengue fever evaluation. A dengue infection will be considered virologically confirmed by either positive polymerase chain reaction (PCR) or NS1 enzyme-linked immunosorbent assay (ELISA). A blood sample will be collected within  $\leq 5$  days after the

[figure not shown]
onset of fever to perform virological confirmation of dengue and for hematology and for biochemistry to assess the severity of infection.

Blood samples for the measurement of neutralizing antibodies (immunogenicity) will be collected from a randomly selected subset of 600 subjects (100 subjects in group 1 and group 4 and 200 subjects in group 2 and group 3). CCI [REDACTED]

[REDACTED] Samples for immunogenicity will be taken prior to vaccination and at intervals of 1, 3, 6, 12, 13, 18, 24, 36, and 48 months following the first vaccination. CCI [REDACTED]

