**Figure 4.a Schematic of Trial DEN-204**

**Investigational Vaccine(s):**

The Investigational Product is TDV, a tetravalent dengue vaccine comprised of four recombinant, live attenuated dengue virus strains:

CCI [REDACTED]

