#### 7.4 Demographic and Baseline Characteristics

Demographic and baseline characteristics will include age, sex, race, weight, height and BMI, which is calculated based on both weight and height measurements from baseline, and will be summarized descriptively by group overall and within each age stratum based on the randomized set and PPS.

In addition, the same tables will be produced based on the baseline seropositive status (seropositive or seronegative). A sample is considered seropositive, if  $MNT_{50} \geq 10$ . A subject who is positive for at least one of four DENV serotypes is categorized as a seropositive subject.

Summary statistics (number of subjects [N], mean, median, SD, minimum, and maximum) will be generated for continuous variables (age, height, weight, BMI and other), and the number and percentage of subjects within each category will be presented for categorical variables (sex, race and other).

Individual demographic data will be presented in the data listing.

Demographic and baseline characteristics of screen failure subjects and reasons for screen failures will be summarized total overall for subjects who are screened, but not enrolled in the trial. Individual demographic data, date of informed consent, any available safety data and reason for screen failure will also be presented in the data listing.

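### The confirmed-dengue table splits time only at Day 30 after the first injection, so early cases after the Month 3 live dose (Group 1) and the Month 12 live booster (Group 3) cannot be picked out

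*SAP*

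**What the plan says.** Section 5.2 names the percentage of subjects with febrile episodes of virologically confirmed dengue as a secondary safety endpoint, in all subjects and over the whole trial. Section 7.2 assesses it in the full Safety Set.

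Section 7.11.5 says that this percentage "will be summarized by group and by baseline seropositive status". It gives three time categories: onset before Day 30, then "2) number of virologically confirmed dengue cases with onset on or after Day 30", then the total. Section 7.1 fixes the origin of the day count: "Trial Day 1 is defined to be the date of the first vaccination". Section 7.11.5 does not redefine it.

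Section 4.4 describes the vaccine as "comprised of four recombinant, live attenuated dengue virus strains". All subjects are injected at Days 1, 91 and 365. After Day 1, the active injections are Day 91 in Group 1 and Day 365 in Group 3. All other later injections are placebo.

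For unsolicited adverse events, Section 7.11.1 lists separate periods after vaccinations 1, 2 and 3.

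On serostatus, Section 7.4 states: "A subject who is positive for at least one of four DENV serotypes is categorized as a seropositive subject". Section 4.4 says that samples for neutralizing antibodies "will be collected from a randomly selected subset of 600 subjects". The schedule for the other subjects (Table A-2) shows no blood sample except the one for febrile illness.

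**The concern.** A cut at Day 30 sets apart dengue that begins soon after an injection. Because the clock starts at the first vaccination, it does so for one injection out of three. The SAP gives no reason for the cut, but an interest in early cases after a first live dose would extend to a second live dose and to a live booster. In the planned table, a case one week after either of these is placed with cases arising up to three years later.

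The same category joins the time before and after Month 12 in Group 3. That group holds 1,000 of the 1,800 subjects, and Section 6.0 gives the effect of a booster and an adequate safety database among the reasons for the sample size. A reader of the safety table would want to see cases before and after the booster separately, and could not.

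A smaller matter is that the table is also to be given by baseline serostatus, in a population where most subjects have no baseline titer, and no denominator is stated.

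**Working it through.** **Inputs (SAP).** Follow-up from Day 1 to Day 1460; injections at Days 1, 91 and 365; cut at Day 30 (Sections 4.4 and 7.11.5). Group sizes and subset sizes come from Table 4.a. Days are nominal and counted inclusively. The ±15-day visit windows are ignored.

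**Check of the plan's own figures.** The SAP states "Subjects will be randomized to these 4 groups in a 1:2:5:1 ratio". The ratio sums to 9 and 1,800 / 9 = 200, which gives 200, 400, 1,000 and 200, as in Table 4.a. The subset is 100 + 200 + 200 + 100 = 600, also as stated.

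**Width of the category from Day 30 on.**
- 1460 − 30 + 1 = 1,431 days; 1,431 / 1,460 = 98.0% of follow-up.
- Group 1: Days 30–90 = 61 days before the second live dose; Days 91–1460 = 1,370 days from it on.
- Group 3: Days 30–364 = 335 days before the booster (335 / 1,431 = 23.4%); Days 365–1460 = 1,096 days from it on (76.6%).

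**Size of the early windows that are lost.** Onset before Day 30 means Days 1–29, which is 29 days with the injection day as the first. The matching windows are Days 91–119 after injection 2 and Days 365–393 after injection 3. Each makes up 29 / 1,431 = 2.0% of the category it falls into.

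**What a split by injection would show.**

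| Injection | Under 30 days | 30 days or more, to next injection or end |
|---|---|---|
| 1 | Days 1–29 (29) | Days 30–90 (61) |
| 2 | Days 91–119 (29) | Days 120–364 (245) |
| 3 | Days 365–393 (29) | Days 394–1460 (1,067) |

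The six cells sum to 1,460. The cells from Day 30 to Day 364 sum to 61 + 29 + 245 = 335, and those from Day 365 on to 29 + 1,067 = 1,096, so the time before and after Month 12 is recovered in every group.

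**Do other outputs supply the split?** The interim analyses cut at Month 6 (Day 180) and Month 18 (Day 540). The band up to Day 180 contains the Day 91 dose, and the band from Day 181 to Day 540 contains the Day 365 booster. Neither cut falls at a later live dose.

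**Serostatus.** Subjects without a planned baseline MNT50 number 1,800 − 600 = 1,200 (66.7%). By group this is 100 of 200, 200 of 400, 800 of 1,000 and 100 of 200, or 50%, 50%, 80% and 50%.

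**The case against.** The table delivers the declared endpoint, which is the percentage of subjects over the whole trial. The Day 30 split is an addition, and no stated aim is breached by leaving out others. The trial is descriptive (Section 6.0), efficacy analysis is marked as not applicable (Section 7.8), and all data are listed by subject and date (Section 7.1), so onset relative to each dose can be recovered. All of this stands, and it makes the point a modest one. It does not remove it: in a descriptive trial the tables are the main output, and a split fixed before unblinding is worth more than one rebuilt from listings.

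Four stronger readings are tempting, and the SAP does not support them.

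- A reader might infer that the table gives a diluted estimate of the booster's effect on dengue. No objective or endpoint compares dengue incidence between Groups 3 and 2 and no such ratio is planned, so there is no estimate to be biased.
- A reader might infer that fever with vaccine virus will be counted as dengue. The SAP says only that PCR or NS1 ELISA confirms a case. It does not say whether the assays tell vaccine virus from wild-type virus, and such detail commonly sits outside a SAP.
- A reader might infer that two later live doses are pooled. No group receives live vaccine at both Month 3 and Month 12, and the table is by group.
- A reader might infer that the serostatus table cannot be produced or will carry wrong percentages. It can be filled for the 600 subset subjects, who are randomly selected. Percentages would go wrong only if Safety Set totals were used as denominators, and nothing says that they will be.

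**Conclusion.** The point holds as an inexpensive improvement to a secondary safety table. With days counted from the first vaccination, the single cut at Day 30 leaves early cases after the Group 1 second dose and the Group 3 booster indistinguishable from cases at any other time within 1,431 days. It also merges Group 3's 335 pre-booster days (23.4%) with 1,096 later days. These figures rest on nominal visit days and full follow-up; actual injection dates will shift them slightly.

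How many cases are affected cannot be said, because the SAP gives no expected dengue incidence. The missing serostatus denominator is a matter of clarification only.

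**What to change.** In Section 7.11.5, keep the three existing categories. Add, by group, the count and percentage of confirmed dengue with onset under 30 days and 30 days or more after each of the three injections. Each interval ends at the next injection or at the end of follow-up, and the denominator is the subjects who received that injection. Count the day of injection as day 1, so that the early row for injection 1 equals the existing first category. A footnote should say that for a subject who misses the Month 12 injection, later cases stay in the rows of the last injection received.

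For the version by baseline serostatus, state that it covers only subjects with a baseline MNT50 result and uses them as the denominator (planned 100, 200, 200 and 100, out of 200, 400, 1,000 and 200), and say so in the table title.

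The cost is SAP wording and table shells. The onset and injection dates that the split needs are already recorded. The downside is some extra rows, several with small counts.
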